#### Recording of adverse events

AEs occurring during this timeframe must be recorded, assessed, reported, analysed and managed in accordance with the UK Policy Framework for Health and Social Care Research and the study protocol. All AEs must be assessed for seriousness.

#### Recording and reporting of serious adverse events

Where an SAE requires recording; full details including the nature of the event, start and stop dates, severity, relationship to research product and/or trial procedures, and the outcome of the event will be recorded in the patient's medical notes and CRFs.). These events will be monitored and followed up until satisfactory resolution and stabilization.

SAEs should be assessed to determine if the event is related to the MRI scanning procedures and assessed for expectedness against the list of expected events detailed below.

Where an event meets the criteria of an SAE and is both:

Related: that is, it resulted from administration of study medicines or any of the research procedures,

And

Unexpected: that is against the procedure events listed below as an expected occurrence.

The SAE is considered a Related and Unexpected Serious Adverse Event (RUSAE) and must be reported to the Sponsor.

The assessment of causality and expectedness must be carried out by an authorised clinician.

#### Expected events related to the MRI scanning procedure

The MRI procedure is painless and not uncomfortable. The primary risks known to occur from MRI are due to the magnet's ability to pull metal objects towards it. This pull can cause metal objects in the body (e.g. surgical clips or staples) to move and cause bleeding or disruption of surrounding tissue. Metal objects carried or worn by a person (e.g. jewellery, hair clips, tools) can be pulled towards the magnet and, if free to fly through the air, could strike an individual. The MRI can cause pacemakers or stimulators implanted in the body to malfunction. There may be some slight discomfort from noise produced by the MRI machine.

Prior to inclusion in the study, the presence of potential MR risks, such as pacemakers, surgical clips or metallic surgical devices will be excluded by medical and surgical history using a standard review form. Participants will be asked to complete and sign a safety screening form and will be instructed to bring or wear clothing without metal fasteners, and remove jewelry and any other metal objects from their body. Participants will wear foam earplugs or headphones to reduce the loud noises made by the scanner. During the performance of MRI, the volunteers will be monitored at all times by research personnel associated with the project. They will be able to communicate with the examiner and, if needed, can terminate or take a break from the procedure at any time

#### Reporting to the Sponsor

All RUSAEs must be reported to the Pharmacovigilance Office immediately (within 24 hours) using the generic non-CTIMP SAE form which is available from [http://www.glasgowctu.org/data/SAE\\_non-](http://www.glasgowctu.org/data/SAE_non-)

CTIMP.pdf. The SAE form should be completed and signed by appropriately delegated staff. The form should be faxed or e-mailed to the PV Office ([contact]) and a copy placed in the Study Site File. If necessary a verbal report can be given by contacting the PV Office on [name]. This must be followed up as soon as possible with a signed written (or electronic) report.

If all of the required information is not available at the time of initial reporting, the investigator must ensure that any missing information is forwarded to the PV Office as soon as this becomes available. The report should indicate that this information is follow-up information for a previously reported event.

The Sponsor in liaison with the CI will carry out an assessment of expectedness prior to submission of the event to the REC.

#### Reporting of RUSAEs to the Ethics Committee

The PV office will report all RUSAEs to the ethics committee within 15 days of the PV office becoming aware of the event, via the 'report of serious adverse event form' for non-CTIMPs published on the Health Research Authority web site. <http://www.hra.nhs.uk/documents/2015/02/safety-report-form-non-ctimp.docx>. The form will be completed by the Sponsor and will be signed by the Chief Investigator prior to submission.

#### Reporting of SAEs related to olumiant to the MAH

The investigators must report all serious adverse events that are suspected to be related to olumiant within 15 days of becoming aware of the event. SAEs can be submitted using the Sponsors generic SAE reporting form that can be downloaded from the following location <https://glasgowctu.org/Home/00-safety-reporting/>.

## 7 STATISTICS AND DATA ANALYSIS

### 7.1 STATISTICAL ANALYSIS PLAN

The study will have a comprehensive Statistical Analysis Plan, which will govern all statistical aspects of the study, and will be agreed by the Trial Management Group (TMG).. To assess whether treatment with Olumiant results in a reduction in functional connectivity (DMN-Insula and DAN-IPL) and glutamate quantification, changes in our neuroimaging metrics of interest between time points will be evaluated using paired t-tests. Changes in pain, clinical phenotyping and immunophenotyping measures will be correlated with those significant regions identified from our primary objective. Putative confounders will be explored using general linear models.

### 7.2 PRIMARY EFFICACY ANALYSIS

The primary outcomes are changes in brain functional connectivity (DMN-Insula and DAN-LIPL) and changes in insular glutamate signal from baseline (day 0) to Visit 2 (week 12), following Olumiant treatment in RA.

Resting state fMRI data will be pre-processed to control transient head movements and parcellated into cortical areas and subcortical nuclei before estimation of a functional connectivity matrix for each subject under each treatment condition. Topological analysis of weighted graphs derived from these matrices will estimate brain network properties such as weighted nodal degree and modular community structure,

which are known to be sensitive to the effects of peripheral CRP and are hypothetically expected to be indicative also of the effects of Olumiant treatment on functional brain networks.

Objective 1 and 2: To assess whether treatment with Olumiant results in a reduction in functional connectivity (DMN-Insula and DAN-IPL) and glutamate levels, changes in our neuroimaging metrics of interest between time points will be evaluated using paired t-tests.

### **7.3 SECONDARY EFFICACY ANALYSIS**

The secondary outcomes are changes in pain, clinical phenotype, peripheral immune markers and their change with MRI markers indicative of CNS pathway function from baseline (day 0) to Visit 2 (week 12), following Olumiant treatment in RA.

Changes in pain, clinical phenotyping and immunophenotyping measures will be correlated with those significant regions identified from our primary objectives. Putative confounders will be explored using general linear models.

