Inclusion Criteria	
 
• Adults <math>\geq</math> 18 years <math><</math> 75 years.
 
• Clinical diagnosis of RA
 
• Selected to start Olumiant by their usual rheumatology clinical team in line with local guidance (previous failure of at least 2 DMARDs and moderate to severe active disease).
 
• Right-handed (to reduce neuroimaging heterogeneity).
 

Exclusion Criteria	
 
• Inability to provide written informed consent.
 

**SOAR - Exploiting Leading Edge 7T MRI Brain Imaging to Decipher Olumiant's Mode of Analgesic Action in Rheumatoid Arthritis**

GLASGOW CLINICAL TRIALS UNIT

FORM 51.001A

V7.0

	
 
• Severe physical impairment (e.g. blindness, deafness, paraplegia).
 
• Pregnant or breast feeding.
 
• Contraindications to MRI (e.g. severe claustrophobia).
 
• Major confounding neurological disease including Multiple Sclerosis, Stroke, Traumatic Brain Injury, Parkinson's Disease, Alzheimer's Disease
 
• Previous targeted synthetic (e.g. Olumiant, tofacitinib) DMARD exposure.
 
• Co-morbid medical conditions that may significantly impair physical functional status
 
• Medical or psychiatric conditions that in the judgment of study personnel would preclude participation in this study (e.g., malignancy, psychosis, suicidal ideation)
 
• BMI > 40 or unable to lie comfortably in MRI
 

Product, Dose, Modes of Administration	Olumiant will be administered following standard of care guidelines.
Duration of Study Participation	12 weeks
Statistical Analysis	To assess whether treatment with Olumiant results in a reduction in functional connectivity (DMN-Insula and DAN-IPL) and glutamate quantification, changes in our neuroimaging metrics of interest between time points will be evaluated using paired t-tests. Changes in pain, clinical phenotyping and immunophenotyping measures will be correlated with those significant regions identified from our primary objective. Putative confounders will be explored using general linear models.

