## **2 STUDY OBJECTIVES**

- 1) To evaluate the effects of Olumiant on DMN-Insula connectivity and insular glutamate levels in RA (neurobiological markers of fibromyalgia).
- 2) To evaluate the effects of Olumiant on DAN-LIPL connectivity in RA (neurobiological marker of peripheral inflammation).
- 3) To explore the relationship between pain, clinical phenotype, peripheral immune markers and their change with MRI markers indicative of CNS pathway function.

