## 4.2 BRAIN IMAGING PROTOCOLS

### 4.2.1 MRI and MRS Protocols

Subjects will be asked to lie supine in the ultra-high resolution 7T multimodal MRI scanner at The Imaging Centre of Excellence, based in a comprehensive clinical setting in Glasgow. Using a MAGNETOM Terra 7T scanner (Siemens Healthcare, Erlangen, Germany) and a single channel transmit, 32 channel receive radiofrequency head coil (Nova Medical, Wilmington, MA), we will obtain neurobiological surrogate measures of functional connectivity and glutamate:

**1) Functional connectivity** - a resting state BOLD-fMRI scan will be undertaken. Functional connectivity MRI (fcMRI) investigations are conducted with subjects resting in the scanner. Ten minutes of whole-brain resting state fMRI data will be collected using a simultaneous-multi-slice (SMS) echoplanar-imaging (EPI) sequence of factor=3. A whole-brain T1-weighted structural image will also be collected using a twice magnetization-prepared rapid gradient echo (MP2RAGE) sequence. During the resting state, subjects will be instructed not to undertake any particular task and to stay awake with their eyes open on a fixation cross. Whole brain coverage will be performed. Data will be pre-processed and analysed using software such as statistical parametric mapping (SPM) version 12 (SPM12, Wellcome Department of Cognitive Neurology, London, United Kingdom) and the Conn (Cognitive and affective neuroscience laboratory, MIT, Cambridge, USA) functional connectivity toolbox, all running on MATLAB 2017a.

Upon collection of resting state fcMRI data, pre-processing steps will include the removal of physiological artefacts, motion correction, realignment, registration, normalization and smoothing. Connectivity indices will be generated from matrices informed by our a priori determined regions of interest (DMN-Insula and DAN-IPL).

**2) Glutamate Imaging** – a magnetic resonance spectroscopy scan will be undertaken in order to detect the glutamate concentration. A single voxel sequence will be employed with semi-LASER preparation. A 20x20 mm^3 voxel will be placed in the R posterior insula and shimming of the static magnetic field will be performed using advanced methods best suited to MRS acquisition at 7T, such as FASTMAP. Spectra will be analysed and quantified in JMRUI or LCModel.

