### **7.6 SAMPLE SIZE**

Based on the only previous study to examine and evidence fMRI changes pre- and post- RA treatment ( $n=10$ ) and our previous MRS study in fibromyalgia ( $n=17$ ) we estimate that a group sample size of  $n=20$  will be sufficient to detect significant neuroimaging changes ( $n=3$  dropout). Moreover, the enhanced sensitivity of 7T and our capacity to apply hypothesis-based region of interest analysis, based on our recent work, will afford greater reserves of power which in turn will enable testing of putative confounders. A sample size of  $n=17$  should be sufficient to measure changes in our optimal outcomes (fMRI and MRS)

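### The imaging-to-pain correlations are planned only for metrics whose mean change is significant, although Objective 3 sets no such condition

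*Combined protocol and SAP*

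**What the plan says.** Section 2 gives the third objective as: "To explore the relationship between pain, clinical phenotype, peripheral immune markers and their change with MRI markers indicative of CNS pathway function". It does not depend on the result of Objectives 1 and 2. The opening sentence of section 7.3 also lists the secondary outcomes without a condition.

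The analysis that follows is narrower. Section 7.3 says that changes in pain, clinical and immune measures "will be correlated with those significant regions identified from our primary objectives". Section 7.1 has the same rule ("will be correlated with those significant regions identified from our primary objective"), and so does the statistical analysis row of the synopsis.

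Section 7.2 names the test that decides significance: "changes in our neuroimaging metrics of interest between time points will be evaluated using paired t-tests". It also names the metrics tested: "The primary outcomes are changes in brain functional connectivity (DMN-Insula and DAN-LIPL) and changes in insular glutamate signal". That makes three.

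Section 7.6 plans 20 participants with 3 dropouts. It gives no alpha, effect size, SD or target correlation.

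**The concern.** The correlation of changes is the only planned analysis that links imaging change to pain change, and the study is about the mechanism of pain relief. The plan makes that analysis depend on a test of something else. The paired t-test asks whether the average change differs from zero. The correlation asks whether patients who change more on imaging also change more in pain. Some patients may rise and others fall, leaving a mean near zero, while imaging and pain still move closely together. A small sample may also simply miss a real mean change.

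If a primary test is non-significant, the plan yields no estimate of how that metric's change relates to pain, clinical or immune change, although the data will have been collected. Objective 3 would be answered for a selected subset of metrics or, if all three tests miss, for none of the a priori metrics.

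**Working it through.** **Sample size.** Evaluable n = 20 − 3 = 17, and 17/(1 − 3/20) = 20, so the dropout arithmetic agrees. Section 7.6 rests its adequacy on two earlier studies (n=10 and n=17). That claim cannot be reproduced, because the inputs to a power calculation are not given.

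**Assumptions, none from the documents.** Alpha is 0.05. The standardised mean change d (mean change divided by SD of change) is 0.3, 0.5, 0.7 or 0.8. The true correlation between imaging change and pain change is 0.4 or 0.6. Changes are bivariate normal.

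**Step 1: chance that a metric's correlation is not run.** This is 1 − power of the paired t-test. Two-sided power is P(|T| > t crit), with T noncentral t on n − 1 degrees of freedom and noncentrality d√n. At n=17, t crit is 2.120. For d=0.5 the noncentrality is 0.5 × √17 = 2.06 and power is 0.491, so the correlation is not run with probability 0.509.

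| Not run | d=0.3 | 0.5 | 0.7 | 0.8 |
|---|---|---|---|---|
| n=17, two-sided | 79% | 51% | 23% | 13% |
| n=17, one-sided 0.05 | 68% | 37% | 13% | 7% |
| n=20, two-sided | 75% | 44% | 16% | 8% |

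The one-sided row is shown because the stated aim is a reduction. Two-sided power of 80% at n=17 needs d = 0.72.

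**Step 2: chance that all three metrics are dropped, n=17, two-sided.** If independent with equal d, this is (1 − power)³; for d=0.3, 0.786³ = 0.486. If the metrics' changes correlate at 0.5 (illustrative), it was simulated.

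| All three dropped | d=0.3 | 0.5 | 0.7 | 0.8 |
|---|---|---|---|---|
| Independent | 49% | 13% | 1% | 0.2% |
| Correlated at 0.5 | 58% | 25% | 6% | 2% |

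**Step 3: chance that a real correlation is both examined and found significant.** Simulation, at least 100,000 samples per scenario. The paired t-test acts as the filter, followed by a two-sided 0.05 test of Pearson's r (critical |r| = 0.482 at n=17).

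| True r, n | No filter | d=0.3 | 0.5 | 0.7 | 0.8 |
|---|---|---|---|---|---|
| 0.6, n=17 | 76% | 15% | 36% | 58% | 66% |
| 0.4, n=17 | 37% | 7% | 17% | 27% | 31% |
| 0.6, n=20 | 84% | 20% | 46% | 70% | 77% |

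These are joint probabilities. Once the filter is passed, power at r=0.6, n=17 is 70% to 75% across these values of d, so nearly all the loss comes from correlations not being run.

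**Step 4: bias and precision.** With a true correlation of zero, the false-positive rate among correlations that are run stays near 5%. With r=0.6 and d=0.3, the mean observed r is 0.56 with the filter and 0.59 without. The filter therefore does not inflate the correlations; its cost is missing estimates. Precision is low in any case. For an observed r of 0.6 at n=17, Fisher's z is 0.693 with standard error 1/√14 = 0.267, giving a 95% interval for r of 0.17 to 0.84.

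**The case against.** - **The text never says only.** One can read it as silent on the other metrics. But this is the sole analysis offered for Objective 3, it is stated three times, and nothing supplied says that other metrics will be correlated. The general linear models are for confounders and do not fill the gap. If no filter was meant, the same words need correcting.
- **The term regions is undefined.** It may fit the parcellated areas and nodal graph measures in section 7.2 better than metrics fixed in advance. This ambiguity is real. But section 4.2.1 uses the same word for the a priori connections, and the phrase refers to the primary objectives, which concern the three metrics, so they still fall under it.
- **A separate SAP will govern the analysis.** It could lift the restriction. It is not among the documents supplied, and a SAP that followed this text would inherit the rule.
- **The sequence follows the hypothesis in section 1.3.** If the drug acts through these markers, they should move. That is a sound reason for care in interpreting a correlation when the mean did not move, but not for leaving it unestimated.
- **Removing the filter adds tests.** Section 4.3.2 has 20 clinical, ultrasound and sensory-testing lines plus cytokines. Three metrics × 20 = 60 correlations, and 60 × 0.05 = 3 nominal positives expected if nothing is related. This stands as a reason to label, count and, if wanted, adjust the results. The filter does not solve it, since a metric that passes is still set against the whole list.

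**Conclusion.** The concern holds. The analysis of Objective 3 carries a selection rule that the objective lacks, and nothing supplied lifts it. The size depends wholly on assumed effect sizes. At n=17 and two-sided 0.05, the rule would withhold a metric's correlation about half the time at d=0.5 and about four times in five at d=0.3, but only 13% of the time at d=0.8 and less beyond that. The harm is incomplete reporting; no false positive findings are alleged. The t-tests for Objectives 1 and 2 always run and are unchanged. The correlations remain exploratory and cannot prove mediation in a single arm. This should be fixed because it is cheap and bears on the analysis closest to the study's question.

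**What to change.** In section 7.1, section 7.3 and the synopsis, replace the reference to significant regions with: *the change in each of the three a priori metrics (DMN-insula connectivity, DAN-LIPL connectivity, insular glutamate), whether or not its mean change is significant*. Carry the same wording into the SAP.

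Report the correlations as exploratory, with confidence intervals, and state how many were run. If the nodal measures in section 7.2 are also to be correlated, say so separately and give their selection rule. Optionally, name a few key pairs in advance, stating which pain rating is meant (the 7-day diary or the Pain Number Rating Scale), or apply a false-discovery-rate adjustment.

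The cost is one phrase in three places, handled as a protocol amendment under section 12. It uses data already being collected and has no effect on patients, sample size or the primary tests. The downside is more correlations to report, which stating their number makes visible.

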### **7.4 SAFETY ANALYSIS**

The safety data (serious adverse events) – both numbers of subjects and events – will be summarised overall using descriptive statistics.

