### **6.3 RECORDING AND REPORTING OF ADVERSE EVENTS**

Reports of Serious Adverse Events (SAE), drug exposure during pregnancy, non-serious Adverse Events (AE) and misuse and abuse of the study drug, other medication errors and uses outside of what is foreseen in the protocol (irrespective if a clinical event has occurred) should be submitted to the Research Ethics Committee (REC) using the Non-CTIMP safety report to REC form.

Only reports of SAEs and non-serious AEs that are 1. related to the study (i.e. they resulted from administration of any of the research procedures) and 2. unexpected (i.e. not listed in the protocol as an expected occurrence) should be submitted.

These should be sent within 15 days of the CI becoming aware of the event. There is no requirement for annual safety reports in addition to the information provided through the annual progress report.

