#### **Recording and reporting of adverse events**

The study is considered to be of low risk and is primarily an observational study. The MRI scanning procedure is the principal trial specific procedure and safety reporting will be focussed around this procedure

Adverse events and serious adverse events will be collected only during the period of time the participant attends clinic for their MRI scan i.e. from the time the participant begins preparation for the scan until 24 hours post scan.

In addition to Sponsor requirements the investigators have a contractual agreement with the MAH to report any SARs suspected to be related to olumiant within 15 days of investigator awareness. These events should be recorded and reported in line with the manufacturers requirements.

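### Section 6.3 says adverse events collected around the scan must be analysed, but Section 7.4 summarises serious events only, so the non-serious ones have no planned summary

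*Combined protocol and SAP*

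**What the plan says.** Section 6.3, under *Recording and reporting of adverse events*, sets what is collected: "Adverse events and serious adverse events will be collected only during the period of time the participant attends clinic for their MRI scan", that is, "from the time the participant begins preparation for the scan until 24 hours post scan". It gives the reason: "The MRI scanning procedure is the principal trial specific procedure and safety reporting will be focussed around this procedure".

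The next subsection, *Recording of adverse events*, says what must happen to these events: "AEs occurring during this timeframe must be recorded, assessed, reported, analysed and managed in accordance with" the UK research governance framework and the protocol. It then asks for a seriousness assessment of every AE.

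The opening of Section 6.3 limits what goes to the Research Ethics Committee (REC): "Only reports of SAEs and non-serious AEs that are 1. related to the study", and that are also unexpected.

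Section 7.4 is the whole of the planned safety analysis. Its subject is "The safety data (serious adverse events", with nothing else inside the bracket. Counts of participants and of events "will be summarised overall using descriptive statistics".

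The schedule of assessments ticks the 7T scan at both visits but AE recording at Visit 2 only. The visit lists in Sections 4.1.1 and 4.1.2 do not mention AE recording at all.

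**The concern.** The protocol sets up collection of non-serious events and says they are to be analysed, but the analysis section defines the safety data without them. A statistician who programs Section 7.4 as written will produce a table of serious adverse events (SAEs) and stop there.

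In a small study with short collection windows, non-serious events are the ones most likely to be seen. Section 6.3 itself lists one as expected: "There may be some slight discomfort from noise produced by the MRI machine". Because it is expected, that event would not go to the REC, and because it is not serious, it would not enter the Section 7.4 summary. If the SAE table is empty, it could be read as showing no safety findings while recorded events sit unused in the database.

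The tick at Visit 2 only raises a further question: whether events around the baseline scan are recorded at all.

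**Working it through.** The documents state no safety figure, so there is none to reproduce. The check is mainly a comparison of text, followed by a calculation of scale.

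**Step 1: follow each type of event through the plan.**

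| Stage | Serious AEs | Non-serious AEs | Place |
|---|---|---|---|
| Collected in the scan window | Yes | Yes | 6.3, *Recording and reporting of adverse events* |
| To be analysed | Yes | Yes | 6.3, *Recording of adverse events* |
| Individual report to the REC | If related and unexpected | If related and unexpected | 6.3, opening |
| Planned summary | Yes | None | 7.4 |

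The term AEs in the second row must include non-serious events, since the same subsection requires each AE to be assessed for seriousness. The gap is in the last row only.

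**Step 2: count the scan windows.** The synopsis gives 20 participants, Section 4.1 gives two visits, and Section 7.6 allows for 3 dropouts.

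- No dropout: 20 × 2 = 40.
- All three dropouts have only the baseline scan: 20 + 17 = 37.
- Schedule read literally, with AEs recorded at Visit 2 only: 17 to 20.

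**Step 3: scale under assumed rates.** The documents give no event rate, so every rate below is an assumption. Windows are treated as independent. With n windows and rate p per window, expected events = n × p and P(at least one) = 1 − (1 − p)^n.

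| Type | Assumed p | Expected, n = 40 | P(at least one), n = 40 | Expected, n = 37 | P(at least one), n = 37 |
|---|---|---|---|---|---|
| Serious | 0.1% | 0.04 | 3.9% | 0.037 | 3.6% |
| Serious | 1% | 0.4 | 33% | 0.37 | 31% |
| Non-serious | 2% | 0.8 | 55% | 0.74 | 53% |
| Non-serious | 5% | 2 | 87% | 1.85 | 85% |
| Non-serious | 10% | 4 | 98.5% | 3.7 | 98% |
| Non-serious | 20% | 8 | over 99.9% | 7.4 | over 99.9% |

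For example, (1 − 0.001)^40 = 0.96 and (1 − 0.01)^40 = 0.67. Over this range, the chance that 40 windows contain no SAE is 96% to 67%.

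If AEs are recorded at Visit 2 only, the expected non-serious count at 5% falls to 17 × 0.05 = 0.85 up to 20 × 0.05 = 1.

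**The case against.** The strongest reply is that the two sections need not conflict. The sentence in Section 6.3 is general safety-reporting language: it ties analysis to the governance framework and the protocol and specifies no table. It can be read as handling each event individually. Safety is not an objective or endpoint (Sections 2 to 2.2), the drug is given as standard care, and Section 6.3 calls the study low risk. An SAE-only summary could be a deliberate and proportionate choice. Sections 7.1 and 7.7 also promise a separate SAP, whose safety tables are not in these documents and which could add non-serious events.

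Part of this stands. Section 6.3 does not dictate a form of summary, and the SAP may close the gap. But if analysis is to follow the protocol, the protocol's analysis section leaves these events out. A SAP that follows Section 7.4 would inherit the omission. If SAEs only were intended, Section 6.3 should say so.

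Three stronger conclusions that a reader might infer are not supported:

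- *Scan-related events never reach the safety result.* Serious ones in the window are collected and do enter the Section 7.4 summary.
- *Non-serious events go unreported.* Those that are related and unexpected go to the REC. These are individual reports rather than a summary, but they are reports.
- *The SAE table is bound to be empty.* At an assumed 1% per window there is a 33% chance of at least one SAE in 40 windows. Section 6.3 also requires SAEs suspected to be related to Olumiant to be reported to the marketing authorisation holder. Section 7.4 does not restrict its SAEs to the scan window, so these could enter the table too.

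**Conclusion.** The point holds as a narrow gap between collection and analysis: non-serious AEs are collected and said to need analysis, but no text in the documents plans a summary of them. That follows from the wording alone and needs no event rate. The mismatch between the schedule and Section 6.3 on when AEs are recorded is a second, related inconsistency.

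The practical size is small. Whether the omission would hide anything depends on rates the documents do not give. The assumed rates show only that non-serious events are more likely to occur than serious ones in 37 to 40 windows. This is a desirable improvement to the plan, not a threat to its conclusions.

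**What to change.** Reword Section 7.4 along these lines: *All recorded adverse events, serious and non-serious, will be summarised as numbers of participants and events, by visit, seriousness and relatedness, with the number of scans performed as denominator for scan-window events.* Carry the same wording into the SAP. If no analysis of non-serious AEs is intended, correct Section 6.3 instead.

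Do not add a split by individual procedure. No text requires non-serious AEs to be attributed to a particular procedure, collection is timed to the MRI, and sensory testing and ultrasound are optional, so the number of scans would be the wrong denominator for them. Relatedness can be included because the REC filter in Section 6.3 already needs that judgement.

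Reconcile the AE row of the schedule of assessments with Section 6.3, since the scan is done at both visits.

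The cost is one sentence, one small table and a correction to the schedule. Sample size, alpha and the primary analysis do not change.
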